8.0 Dosage Modification Based on Adverse Events

Strictly follow the modifications in this table for the first **two** cycles, until individual treatment tolerance can be ascertained. Thereafter, these modifications should be regarded as guidelines to produce mild-to-moderate, but not debilitating, side effects. If multiple adverse events are seen, administer dose based on greatest reduction required for any single adverse event observed. Reductions or increases apply to treatment given in the preceding cycle and are based on adverse events observed since the prior dose.

ALERT: ADR reporting may be required for some adverse events (See Section 10)

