8.1 Dose Levels (Based on Adverse Events in Tables 8.2)

Brentuximab Vedotin	
	Starting Dose 1.8 mg/kg IV Day 1
1 st dose reduction	1.2 mg/kg IV Day 1
2 nd dose reduction	Discontinue

Nivolumab	
	Starting Dose 3.0 mg/kg IV Day 1
1 st dose reduction	Discontinue

Note: If either drug is discontinued, the patient may continue treatment with the other drug. If both drugs are discontinued, the patient will go to event monitoring per Section 18.0.

8.2 **Recommended Brentuximab Vedotin (BV) and Nivolumab Dose Modifications for Treatment-Associated Toxicity**

→ → Use the NCI Common Terminology Criteria for Adverse Events (CTCAE) version 4.0* unless otherwise specified ← ←			
CTCAE System/Organ/Class (SOC)	ADVERSE EVENT	AGENT	ACTION**
AT TIME OF RETREATMENT			
Investigations	Platelet count decreased	Brentuximab Vedotin (BV) and Nivolumab	Grade 3: Hold both BV and nivolumab until grade 2 or better, then reinstitute BV at 1.2 mg/kg and resume nivolumab at same dose.

→ → Use the NCI Common Terminology Criteria for Adverse Events (CTCAE) version 4.0* unless otherwise specified ← ←			
CTCAE System/Organ/Class (SOC)	ADVERSE EVENT	AGENT	ACTION**
Investigations	
Alanine aminotransferase Increased, Aspartate aminotransferase Increased, and/or Blood bilirubin increased
 
NOTE: increased bilirubin does not factor into dose modifications if secondary to Gilbert's syndrome.
	Brentuximab Vedotin (BV) and Nivolumab	
Grade 2 (>3 to 5 x ULN) AST or ALT elevations: Omit dosing for nivolumab; continue BV at the same dose level. Nivolumab may be resumed if the value improves to Grade 1 (≤ 3 x ULN) or better.
 
Grade 2 Bilirubin elevations (>1.5 to 3 x ULN): Omit dosing for nivolumab; continue BV at the same dose level. Nivolumab may be resumed if the bilirubin improves to Grade 1 (>ULN to 1.5 x ULN) or better.
 
Grade 2 (>3 to 5 x ULN) AST or ALT elevations WITH Grade 2 Bilirubin elevations (>1.5 to 3 x ULN): Hold both nivolumab and BV until ALT/AST value improves to Grade 1 (≤ 3 x ULN) or better and bilirubin value improves to Grade 1 (>ULN to 1.5 x ULN) or better.
 
Grade 3 (AST or ALT, OR Bilirubin elevations): Discontinue nivolumab; hold dosing for BV until toxicity is \leq Grade 2 or has returned to baseline, then resume at the same dose level.
 
Grade 4 (AST or ALT, OR Bilirubin elevations): Discontinue both nivolumab and BV. Patient should go to event monitoring, per Section 18.

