→ → Use the NCI Common Terminology Criteria for Adverse Events (CTCAE) version 4.0* unless otherwise specified ← ←			
CTCAE System/Organ/Class (SOC)	ADVERSE EVENT	AGENT	ACTION**
Investigations	Creatinine Increased	Nivolumab	
Patients will be monitored for elevated serum creatinine prior to and periodically during treatment. Administer corticosteroids at a dose of 1 to 2 mg/kg/day prednisone equivalents followed by corticosteroid taper for life-threatening (Grade 4) serum creatinine elevation and permanently Discontinue nivolumab; continue BV at the same dose level.
 
For severe (Grade 3) or moderate (Grade 2) serum creatinine elevation, withhold nivolumab and administer corticosteroids at a dose of 0.5 to 1 mg/kg/day prednisone equivalents followed by corticosteroid taper; if worsening or no improvement occurs, increase dose of corticosteroids to 1 to 2 mg/kg/day prednisone equivalents and permanently Discontinue nivolumab; continue BV at the same dose level.

Investigations	Neutrophil (ANC) count decreased	Brentuximab Vedotin (BV) and Nivolumab	
≥Grade 3; hold both BV and nivolumab until resolved to grade 1 (or baseline). At this point myeloid growth factors can be used at investigator's discretion.
 
If not resolved to ≤Grade 1 or better within 28 days, discontinue nivolumab and BV. Patient should go to event monitoring per Section 18.

→ → Use the NCI Common Terminology Criteria for Adverse Events (CTCAE) version 4.0* unless otherwise specified ← ←			
CTCAE System/Organ/Class (SOC)	ADVERSE EVENT	AGENT	ACTION**
	Amylase and/or lipase increase	Brentuximab Vedotin (BV) and Nivolumab	Grade ≥ 3: Hold BV and nivolumab until resolved to ≤Grade 2, then resume at same dose, per protocol. If there is clinical or radiographic evidence of pancreatitis, refer to pancreatitis AE actions (below).

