Immune System Disorders	Immune system disorders-other	Nivolumab	
If patient experiences immune-mediated rash Grade 3: Omit nivolumab dose until symptoms resolve and management with corticosteroids is complete, and then restart at the same dose level. If reoccurrence, discontinue nivolumab (continue brentuximab vedotin per protocol).
 
Grade 4: Permanently discontinue nivolumab (continue BV per protocol).
 
For any suspected immune-mediated adverse reactions, exclude other causes. Based on the severity of the adverse reaction, omit nivolumab, administer high-dose corticosteroids, and if appropriate, initiate hormone-replacement therapy. Upon improvement to Grade 1 or less, initiate corticosteroid taper and continue to taper over at least 1 month. Consider restarting nivolumab after completion of corticosteroid taper based on the severity of the event (continue BV per protocol).

Infections and Infestations	Encephalitis infection	Brentuximab Vedotin (BV) and Nivolumab	Discontinue Nivolumab if patient experiences immune-mediated encephalitis. Continue BV at same dose per protocol.

→ → Use the NCI Common Terminology Criteria for Adverse Events (CTCAE) version 4.0* unless otherwise specified ← ←			
CTCAE System/Organ/Class (SOC)	ADVERSE EVENT	AGENT	ACTION**
Nervous system disorders	Peripheral sensory neuropathy or peripheral motor neuropathy	Brentuximab Vedotin (BV)	
Grade 2 Reduce BV by 1 dose level and resume treatment; if already at 1.2 mg/kg, continue dosing at that level.
 
Grade 3 Omit BV until toxicity is ≤ Grade 2, then consult with PI
 
Grade 4 Discontinue BV. Continue Nivolumab at same dose per protocol.

Gastrointestinal disorders	Pancreatitis	Brentuximab Vedotin and Nivolumab	
Grade 2 Omit nivolumab until resolution, maximum 3 weeks. If > 3 weeks, discontinue nivolumab ONLY (continue BV per protocol).
 
Grade 3 or Grade 4, Discontinue BV . Hold nivolumab until grade 1 or better, then reintroduce. If it recurs, then discontinue nivolumab and patient should go to event monitoring, per Section 18.

Gastrointestinal disorders	Diarrhea	Brentuximab Vedotin (BV) and Nivolumab	
Grade ≥2: Hold both BV and nivolumab until resolution to baseline grade
 
Grade 3: Hold both BV and nivolumab and start corticosteroids until resolution to baseline grade.
 
Grade ≥4: Discontinue BV and Nivolumab. Patient should go to event monitoring, per Section 18.

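### From cycle 3, Section 8.0 makes Table 8.2 advisory without expressly keeping its stops for life-threatening toxicity, Grade 3 or higher pneumonitis or immune-mediated encephalitis binding

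*Combined protocol and SAP*

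**What the plan says.** Section 8.0 makes Table 8.2 binding for the first two cycles, "until individual treatment tolerance can be ascertained". It then changes the status of the whole table: "Thereafter, these modifications should be regarded as guidelines to produce mild-to-moderate, but not debilitating, side effects". No row, grade or event is excepted, and the heading of Section 8.2 itself calls the modifications recommended.

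The table contains rows that stop a drug outright. Examples are:

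- Grade 4 AST, ALT or bilirubin: "Discontinue both nivolumab and BV. Patient should go to event monitoring, per Section 18".
- Grade 4 creatinine increase: corticosteroids for the "serum creatinine elevation and permanently Discontinue nivolumab; continue BV at the same dose level".
- Grade 4 immune-mediated rash: "Permanently discontinue nivolumab (continue BV per protocol".
- Encephalitis: "Discontinue Nivolumab if patient experiences immune-mediated encephalitis".
- Grade 4 peripheral neuropathy: "Discontinue BV. Continue Nivolumab at same dose per protocol".
- Grade 3 or 4 pancreatitis: brentuximab vedotin (BV) is discontinued; for the other drug, "Hold nivolumab until grade 1 or better, then reintroduce".

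Grade 4 or higher diarrhea, Grade 4 or higher colitis and Grade 3 or higher pneumonitis each stop both drugs. The table's footnote defines discontinuation as a complete stop of the named drug. It does not say in which cycles the action binds.

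**The concern.** The table is relaxed because two cycles are taken to show how well a patient tolerates treatment. That reasoning suits dose tailoring for moderate toxicity. It does not suit events that can first appear late. The protocol's own nursing guidelines (15.199b and 15.291) say nivolumab effects can be life threatening and can be delayed by months. Section 1.225 describes BV neuropathy as having a cumulative pattern. Two uneventful cycles therefore do not settle tolerance for these events.

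What is at stake is patient safety and consistency between sites. From cycle 3 it is unclear whether stopping for such an event is required or only advised. Section 7.1 says the combination had not been studied before. The patients are 60 or older, or mostly younger patients with reduced cardiac, pulmonary or renal function.

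**Working it through.** No figure in the plan bears on this point, so there is none to reproduce. The check is a reading of the stopping provisions side by side, followed by a count.

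**Does any other available section set a binding stop grade for an individual patient after cycle 2?**

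| Section | What it governs | Binding individual stop for toxicity after cycle 2? |
|---|---|---|
| 7.12 | Dose-limiting toxicity, first cycle only | No |
| 7.222 | Nivolumab may be interrupted, delayed or stopped according to tolerance | No, permissive |
| 8.1 | Dose ladder; where the patient goes when both drugs are off | No grade set |
| 8.2 footnote | Meaning of omit, hold and discontinue | No |
| 13.3 | Where patients go after stopping for unacceptable events | No grade set |
| 16.52 | Suspends accrual to the trial; counts related non-hematologic events of Grade 4 or higher | No; Grade 3 pneumonitis is not counted |

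The plan does write unconditional stops elsewhere: lack of metabolic response or progression (7.5, 13.1) and pregnancy (10.3341). Those show what a binding rule looks like in this document.

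**Discontinuations that should bind in every cycle**

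- Both drugs (4): Grade 4 AST, ALT or bilirubin; Grade 4 or higher diarrhea; Grade 4 or higher colitis; Grade 3 or higher pneumonitis.
- Nivolumab (3): Grade 4 creatinine increase; Grade 4 immune-mediated rash; immune-mediated encephalitis.
- BV (2): Grade 4 peripheral neuropathy; Grade 4 pancreatitis.

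Total: 4 + 3 + 2 = 9. In 3 + 2 = 5 of these the table lets the other drug continue (for pancreatitis, nivolumab after a hold). Only the creatinine and rash rows, 2 of the 9, describe the stop as permanent.

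**Size of the advisory period**

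Inputs: a maximum of 8 cycles (7.4), 21-day cycles 1 to 7 (7.22), and a strict period of 2 cycles (8.0).

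- By dose: doses 3 to 8 are 6 of 8, so 6/8 = 75%.
- By time in which an event can still change a later dose: cycles 1 to 7 give 7 × 21 = 147 days. Cycles 3 to 7 give 5 × 21 = 105 days, and 105/147 = 71%. Cycle 8 is left out because no dose follows its Day 1. This assumes no delays and treats an event arising in cycle 2 as still under the strict rule.
- If the decision on Day 1 of cycle 3 is itself counted as advisory, the figure is 6 of 7 intervals, 126/147 = 86%.

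The strict period is 2 × 21 = 42 days, or 6 weeks. Section 1.33 reports nivolumab steady state by 12 weeks with dosing every 2 weeks. Dosing here is every 3 weeks, so the comparison is only indicative. It does suggest that exposure may still be rising when the table becomes advisory.

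**The case against.** The strongest reply is that 8.0 does not grant open discretion. It states an aim, and re-dosing after Grade 4 hepatic toxicity, Grade 4 colitis or encephalitis does not fit that aim. This stands, and it is the main reason the point is modest. A reader might infer that the protocol permits, or even invites, re-dosing after a life-threatening event. The documents do not support that. They leave the status of the stop unstated while pointing toward stopping.

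A second reply is that key places could not be checked. Section 9.6 refers to Appendix V for further algorithms, and many stop rows refer to Section 18. Neither was available, and their absence here is not a fault of the plan. A reader might conclude that the protocol contains no mandatory stop after cycle 2, but that cannot be said. If Appendix V does require stops, 8.0 should still agree with it.

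Third, 8.1 offers no reduced nivolumab dose, and two rows call the stop permanent, so a specific stop could be read as surviving a general sentence. That is a reasonable inference, but 8.0 does not say so, and seven of the nine rows lack the word. The instruction in 8.0 to apply the greatest reduction when several events occur says which row governs, not whether the table binds.

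Fourth, Section 1.225 also says that phase 2 BV events were mainly mild to moderate and that delay and dose reduction generally managed the neuropathy. That supports tailoring at lower grades. It does not address Grade 4.

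Fifth, a bare list of mandatory stops could suggest that the unlisted ones are optional. This stands, and the fix carries a sentence to prevent it.

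Sixth, a reader might extend the point to BV after Grade 3 pancreatitis, since that row covers Grades 3 and 4. Grade 3 pancreatitis is not shown to be life threatening or immune-mediated, so only Grade 4 is named.

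**Conclusion.** The point holds in a limited form. In the text available, Table 8.2 is advisory for 6 of 8 planned doses, and nothing expressly keeps its stops for Grade 4 events, Grade 3 or higher pneumonitis or immune-mediated encephalitis binding. The aim stated in 8.0 favors stopping but fixes no grade.

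The 75% figure, and the 71% to 86% of between-dose time, measure exposure to an unclear rule. They do not measure risk. The documents give no rate at which investigators would re-dose after such an event, so no number of affected patients can be stated. Expedited reporting of serious events and the twice-yearly safety board review would make divergent practice visible, but neither stops an individual patient's drug. A reader might also infer some effect on the trial's inference. There is none: the primary endpoint, N, alpha and power are untouched.

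The conclusion rests on Section 8.0 being read as written and on Appendix V and Section 18 not having been seen.

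**What to change.** Add to Section 8.0:

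> *The following Table 8.2 discontinuations are mandatory in all cycles: Grade 4 AST, ALT or bilirubin, Grade ≥4 diarrhea or colitis, and Grade ≥3 pneumonitis (both drugs); Grade 4 creatinine increase, Grade 4 immune-mediated rash, and immune-mediated encephalitis (nivolumab); Grade 4 peripheral neuropathy and Grade 4 pancreatitis (BV). This list does not make any other Table 8.2 discontinuation optional in cycles 1–2, and from cycle 3 the other rows remain the recommended action.*

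Align the wording with Appendix V.

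The cost is two sentences of text, with no change to the actions in the table. The real downside is that an investigator can no longer choose to re-dose a responding patient with the named drug after one of these events. Discretion from cycle 3 is kept for the other stops: those resting on a lower-grade laboratory value (Grade 3 liver tests, Grade 2 to 3 creatinine), a nonspecific symptom (cough, dyspnea), failure to resolve, or recurrence, and BV after Grade 3 pancreatitis. The sponsor can add any of these to the list.

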8.1 Dose Levels (Based on Adverse Events in Tables 8.2)

Brentuximab Vedotin	
	Starting Dose 1.8 mg/kg IV Day 1
1 st dose reduction	1.2 mg/kg IV Day 1
2 nd dose reduction	Discontinue

Nivolumab	
	Starting Dose 3.0 mg/kg IV Day 1
1 st dose reduction	Discontinue

Note: If either drug is discontinued, the patient may continue treatment with the other drug. If both drugs are discontinued, the patient will go to event monitoring per Section 18.0.

8.2 **Recommended Brentuximab Vedotin (BV) and Nivolumab Dose Modifications for Treatment-Associated Toxicity**

→ → Use the NCI Common Terminology Criteria for Adverse Events (CTCAE) version 4.0* unless otherwise specified ← ←			
CTCAE System/Organ/Class (SOC)	ADVERSE EVENT	AGENT	ACTION**
AT TIME OF RETREATMENT			
Investigations	Platelet count decreased	Brentuximab Vedotin (BV) and Nivolumab	Grade 3: Hold both BV and nivolumab until grade 2 or better, then reinstitute BV at 1.2 mg/kg and resume nivolumab at same dose.

→ → Use the NCI Common Terminology Criteria for Adverse Events (CTCAE) version 4.0* unless otherwise specified ← ←			
CTCAE System/Organ/Class (SOC)	ADVERSE EVENT	AGENT	ACTION**
Investigations	
Alanine aminotransferase Increased, Aspartate aminotransferase Increased, and/or Blood bilirubin increased
 
NOTE: increased bilirubin does not factor into dose modifications if secondary to Gilbert's syndrome.
	Brentuximab Vedotin (BV) and Nivolumab	
Grade 2 (>3 to 5 x ULN) AST or ALT elevations: Omit dosing for nivolumab; continue BV at the same dose level. Nivolumab may be resumed if the value improves to Grade 1 (≤ 3 x ULN) or better.
 
Grade 2 Bilirubin elevations (>1.5 to 3 x ULN): Omit dosing for nivolumab; continue BV at the same dose level. Nivolumab may be resumed if the bilirubin improves to Grade 1 (>ULN to 1.5 x ULN) or better.
 
Grade 2 (>3 to 5 x ULN) AST or ALT elevations WITH Grade 2 Bilirubin elevations (>1.5 to 3 x ULN): Hold both nivolumab and BV until ALT/AST value improves to Grade 1 (≤ 3 x ULN) or better and bilirubin value improves to Grade 1 (>ULN to 1.5 x ULN) or better.
 
Grade 3 (AST or ALT, OR Bilirubin elevations): Discontinue nivolumab; hold dosing for BV until toxicity is \leq Grade 2 or has returned to baseline, then resume at the same dose level.
 
Grade 4 (AST or ALT, OR Bilirubin elevations): Discontinue both nivolumab and BV. Patient should go to event monitoring, per Section 18.

→ → Use the NCI Common Terminology Criteria for Adverse Events (CTCAE) version 4.0* unless otherwise specified ← ←			
CTCAE System/Organ/Class (SOC)	ADVERSE EVENT	AGENT	ACTION**
Investigations	Creatinine Increased	Nivolumab	
Patients will be monitored for elevated serum creatinine prior to and periodically during treatment. Administer corticosteroids at a dose of 1 to 2 mg/kg/day prednisone equivalents followed by corticosteroid taper for life-threatening (Grade 4) serum creatinine elevation and permanently Discontinue nivolumab; continue BV at the same dose level.
 
For severe (Grade 3) or moderate (Grade 2) serum creatinine elevation, withhold nivolumab and administer corticosteroids at a dose of 0.5 to 1 mg/kg/day prednisone equivalents followed by corticosteroid taper; if worsening or no improvement occurs, increase dose of corticosteroids to 1 to 2 mg/kg/day prednisone equivalents and permanently Discontinue nivolumab; continue BV at the same dose level.

Investigations	Neutrophil (ANC) count decreased	Brentuximab Vedotin (BV) and Nivolumab	
≥Grade 3; hold both BV and nivolumab until resolved to grade 1 (or baseline). At this point myeloid growth factors can be used at investigator's discretion.
 
If not resolved to ≤Grade 1 or better within 28 days, discontinue nivolumab and BV. Patient should go to event monitoring per Section 18.

→ → Use the NCI Common Terminology Criteria for Adverse Events (CTCAE) version 4.0* unless otherwise specified ← ←			
CTCAE System/Organ/Class (SOC)	ADVERSE EVENT	AGENT	ACTION**
	Amylase and/or lipase increase	Brentuximab Vedotin (BV) and Nivolumab	Grade ≥ 3: Hold BV and nivolumab until resolved to ≤Grade 2, then resume at same dose, per protocol. If there is clinical or radiographic evidence of pancreatitis, refer to pancreatitis AE actions (below).
Immune System Disorders	Immune system disorders-other	Nivolumab	
If patient experiences immune-mediated rash Grade 3: Omit nivolumab dose until symptoms resolve and management with corticosteroids is complete, and then restart at the same dose level. If reoccurrence, discontinue nivolumab (continue brentuximab vedotin per protocol).
 
Grade 4: Permanently discontinue nivolumab (continue BV per protocol).
 
For any suspected immune-mediated adverse reactions, exclude other causes. Based on the severity of the adverse reaction, omit nivolumab, administer high-dose corticosteroids, and if appropriate, initiate hormone-replacement therapy. Upon improvement to Grade 1 or less, initiate corticosteroid taper and continue to taper over at least 1 month. Consider restarting nivolumab after completion of corticosteroid taper based on the severity of the event (continue BV per protocol).

Infections and Infestations	Encephalitis infection	Brentuximab Vedotin (BV) and Nivolumab	Discontinue Nivolumab if patient experiences immune-mediated encephalitis. Continue BV at same dose per protocol.

→ → Use the NCI Common Terminology Criteria for Adverse Events (CTCAE) version 4.0* unless otherwise specified ← ←			
CTCAE System/Organ/Class (SOC)	ADVERSE EVENT	AGENT	ACTION**
Nervous system disorders	Peripheral sensory neuropathy or peripheral motor neuropathy	Brentuximab Vedotin (BV)	
Grade 2 Reduce BV by 1 dose level and resume treatment; if already at 1.2 mg/kg, continue dosing at that level.
 
Grade 3 Omit BV until toxicity is ≤ Grade 2, then consult with PI
 
Grade 4 Discontinue BV. Continue Nivolumab at same dose per protocol.

Gastrointestinal disorders	Pancreatitis	Brentuximab Vedotin and Nivolumab	
Grade 2 Omit nivolumab until resolution, maximum 3 weeks. If > 3 weeks, discontinue nivolumab ONLY (continue BV per protocol).
 
Grade 3 or Grade 4, Discontinue BV . Hold nivolumab until grade 1 or better, then reintroduce. If it recurs, then discontinue nivolumab and patient should go to event monitoring, per Section 18.

Gastrointestinal disorders	Diarrhea	Brentuximab Vedotin (BV) and Nivolumab	
Grade ≥2: Hold both BV and nivolumab until resolution to baseline grade
 
Grade 3: Hold both BV and nivolumab and start corticosteroids until resolution to baseline grade.
 
Grade ≥4: Discontinue BV and Nivolumab. Patient should go to event monitoring, per Section 18.

→ → Use the NCI Common Terminology Criteria for Adverse Events (CTCAE) version 4.0* unless otherwise specified ← ←			
CTCAE System/Organ/Class (SOC)	ADVERSE EVENT	AGENT	ACTION**
Gastrointestinal disorders	Colitis	Brentuximab Vedotin (BV) and Nivolumab	
Grade ≥2: Hold both BV and nivolumab until resolution to baseline grade
 
Grade 3: Hold both BV and nivolumab and start corticosteroids until resolution to baseline grade.
 
Grade ≥4: Discontinue BV and Nivolumab. Patient should go to event monitoring, per Section 18.

General disorders and administration site conditions	Fatigue	Brentuximab Vedotin (BV) and Nivolumab	Grade 3: Hold both BV and nivolumab until grade 2 or better
Endocrine Disorders	Adrenal insufficiency Hypothyroidism, Hyperthyroidism, Endocrine Disorders- Other (i.e. Hypophysitis, diabetes)	Nivolumab	Grade ≥3: Omit nivolumab until symptoms resolve and management with corticosteroids (if needed for symptoms of acute inflammation) is complete, and then restart at the same dose level. If reoccurrence, discontinue. (continue BV per protocol). Nivolumab should be continued in the presence of hormone replacement therapy, as long as no symptoms are present.
Respiratory, thoracic and mediastinal disorders	Pneumonitis	Brentuximab Vedotin (BV) and Nivolumab	
Grade ≥2: Hold both BV and nivolumab and start corticosteroids until resolution to baseline grade.
 
Grade ≥3: Discontinue BV and nivolumab and initiate treatment with high doses of corticosteroids. Patient should go to event monitoring, per Section 18.

→ → Use the NCI Common Terminology Criteria for Adverse Events (CTCAE) version 4.0* unless otherwise specified ← ←

CTCAE System/Organ/Class (SOC)	ADVERSE EVENT	AGENT	ACTION**
Respiratory, thoracic and mediastinal disorders	Cough	Brentuximab Vedotin (BV) and Nivolumab	Grade ≥2: Hold both BV and nivolumab and start corticosteroids until resolution to baseline grade. Grade ≥3: Discontinue BV and nivolumab and initiate treatment with high doses of corticosteroids. Patient should go to event monitoring, per Section 18.
Respiratory, thoracic and mediastinal disorders	Dyspnea	Brentuximab Vedotin (BV) and Nivolumab	Grade ≥3: Hold both BV and nivolumab up to four weeks until resolution to baseline grade. If no resolution patient should go to event monitoring, per Section 18.
All other hematologic and non-hematologic	All other hematologic and non-hematologic	Brentuximab Vedotin (BV) and Nivolumab	Grade ≥ 2: Hold both BV and Nivolumab up to four weeks until resolution to Grade 1 or baseline. If no resolution patient should go to event monitoring, per Section 18.

* Located at http://ctep.cancer.gov/protocolDevelopment/electronic_applications/ctc.htm

** Use the following to describe actions in the Action column:

- Omit = The current dose(s) for the specified drug(s) during a cycle is skipped. The patient does not make up the omitted dose(s) at a later time.
- Hold/Delay = The current dose(s) of all drugs during a cycle is delayed. The patient does make up the delayed dose(s) when the patient meets the protocol criteria to restart drugs.
- Discontinue = The specified drug(s) are totally stopped.

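### The Section 8.2 platelet row covers Grade 3 only, so no reduced brentuximab vedotin restart dose is stated after Grade 4

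*Combined protocol and SAP*

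**What the plan says.** The platelet row of Section 8.2 has a single line: "Grade 3: Hold both BV and nivolumab until grade 2 or better, then reinstitute BV at 1.2 mg/kg and resume nivolumab at same dose". It has no Grade 4 line and no sign that Grade 3 means Grade 3 and above.

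The last row of the table covers all remaining hematologic and non-hematologic events. For Grade 2 or worse it says "Hold both BV and Nivolumab up to four weeks until resolution to Grade 1 or baseline", and patients who do not recover go to event monitoring. It names no restart dose. The footnote to the table defines a hold as a delayed dose that is later made up, and the definition includes no reduction.

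Other laboratory rows reach Grade 4. The neutrophil row is written for Grade 3 and above, and so is the amylase/lipase row: "Grade ≥ 3: Hold BV and nivolumab until resolved to ≤Grade 2, then resume at same dose, per protocol". The liver row has its own Grade 4 line.

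Section 8.0 makes the table binding for the first two cycles and a guideline after that. It also says that, when several adverse events occur, the largest reduction called for by any one of them sets the dose, and that changes rest on events seen since the last dose. Section 8.1 sets the BV starting dose at 1.8 mg/kg and the first reduction at 1.2 mg/kg.

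**The concern.** A dose table should not become more permissive as the toxicity gets worse. Here the reduction to 1.2 mg/kg is written for Grade 3 and for no other grade. A site following the table to the letter after Grade 4 finds no instruction to reduce BV.

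The plan expects this event. Section 10.32 lists platelet decreases up to Grade 4 among the events expected in this population and exempts them from expedited reporting unless the patient is hospitalized. The adverse event stopping rule in Section 16.52 counts non-hematologic events only. Section 7.12 makes a related Grade 4 hematologic event in cycle 1 a dose-limiting toxicity, but that rule governs the cohort and does not set the individual patient's next dose.

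At stake are the restart dose for the individual patient and consistency between sites.

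**Working it through.** The plan gives no figure to reproduce. The check sets the relevant lines side by side and then sizes the difference in dose.

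**Step 1: what each possible rule gives.**

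| Case | Recovery needed | Time limit | BV restart |
|---|---|---|---|
| Grade 3, platelet row | Grade 2 or better | none stated | 1.2 mg/kg |
| Grade 4, if the catch-all row applies | Grade 1 or baseline | four weeks | no reduction stated |
| Grade 4, if the catch-all row is only for events not named above it | none stated | none stated | none stated |

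The documents do not say which of the last two rows of this comparison applies. Sending an unlisted grade of a named event to the catch-all row is an inference. It also has a side effect: Grade 2 platelets would go there too and be held to Grade 1 or baseline, although the Grade 3 line restarts treatment at Grade 2. Neither reading supplies a BV reduction after Grade 4.

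**Step 2: does another section supply it?**

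- Section 8.0: the largest-reduction rule is written for several events occurring together. It does not say that a lower grade of the same event supplies the reduction for a higher grade. Basing changes on events since the last dose helps, because a count recovering from Grade 4 passes through Grade 3, but Section 8.0 does not draw that conclusion.
- Sections 7.1 and 16.4: the weekly investigator call, prompt contact after a dose-limiting toxicity and the accrual halt make divergent restarts less likely in the safety phase. None states a restart dose.
- Section 9.6 points to Appendix V for further management algorithms. That appendix was not among the documents available, so it could not be checked.

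**Step 3: size of the difference.** Inputs: 1.8 and 1.2 mg/kg (Section 8.1); BV capped at 180 mg, equivalent to 100 kg (Sections 7.22 and 15.13); 80 kg as a reference weight, the approximate median in nivolumab trials (Section 1.33).

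- Ratio: 1.8 / 1.2 = 1.5.
- At 80 kg: 1.8 × 80 = 144 mg; 1.2 × 80 = 96 mg; difference 48 mg.
- At the cap: 1.8 × 100 = 180 mg; 1.2 × 100 = 120 mg; difference 60 mg.

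**Step 4: how often.** Section 1.226 reports platelet shifts to Grade 3 or worse in 6% of BV phase 2 patients. Section 15.27 gives 1% to 3% for Grade 3/4 thrombocytopenia with nivolumab. Both figures combine Grades 3 and 4 and are for single agents, so no Grade 4 frequency for the combination can be derived.

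**The case against.** The strongest reply is that the plan already points to 1.2 mg/kg. Every recovering Grade 4 count passes through Grade 3, and Section 8.0 tells sites to act on events since the last dose and to prefer the largest reduction. This stands as evidence of what a sensible site would do. It does not stand as a written rule, and the first two cycles are where the plan leaves least room for judgment.

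A second reply is that the catch-all row is not lax. It demands fuller recovery than the Grade 3 line and adds a four-week limit, after which treatment ends. That is correct, and it means Grade 4 is not handled less protectively in every respect; only the restart dose is at issue. Restarting without a reduction is also not foreign to the table. The neutrophil row states no reduction and the amylase/lipase row resumes at the same dose. But those rows ask for no reduction at Grade 3 either, so nothing is reversed in them. The fatigue row also names only Grade 3, and it too requires no reduction.

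Third, 1.8 mg/kg is the protocol's own starting dose, and no harm from it after Grade 4 platelets is shown. That is accepted, and it limits how much weight the point can bear.

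**Conclusion.** The gap is real and small. No line states a BV reduction after Grade 4 platelets, while Grade 3 requires one. Read literally, the restart could be 1.5 times the dose required after the milder event, which is 48 mg more at 80 kg and 60 mg more at the cap. This rests on the text of Sections 8.0 to 8.2 and assumes that Appendix V does not settle the matter. Frequency is unknown. No effect on the primary endpoint, power or alpha follows.

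A reader might infer three stronger things that the documents do not support:

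- **That the plan directs 1.8 mg/kg after Grade 4.** It does not. It is silent on the dose, and Section 8.0 leans the other way.
- **That BV must stop if a platelet event occurs at 1.2 mg/kg, because Section 8.1 lists discontinuation as the second reduction.** The neuropathy row keeps Grade 2 patients already at 1.2 mg/kg on that dose, so the second step is not automatic.
- **That the liver row has a comparable defect.** A patient improving from Grade 3 to Grade 2 on both transaminases and bilirubin meets one line that resumes BV and another that holds it. This is a narrow case, and the table heading "AT TIME OF RETREATMENT" already favors holding.

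**What to change.** Rewrite the platelet row for Grade 3 or higher, with BV restarted at 1.2 mg/kg and nivolumab at the same dose. Within the row, keep the present recovery target for Grade 3 (Grade 2 or better). For Grade 4, require recovery to Grade 1 or baseline within four weeks, otherwise event monitoring. The Grade 4 target needs to be written out: simply widening the row would relax it to Grade 2 for anyone who now reads Grade 4 as covered by the catch-all row. Check that Appendix V agrees.

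The change is an amendment to one row, with no added procedures, visits or patients. The clinical cost is a lower BV dose in the few patients with Grade 4 platelets who would otherwise have restarted at 1.8 mg/kg. If the sponsor had regarded Grade 4 as outside the catch-all row, the four-week limit would also be new for those patients.
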